#### 5.15 Management of Radiation Necrosis

When early signs of progressive parenchymal changes are present on imaging we will consider referral for hyperbaric oxygen therapy (HBOT). HBOT may be recommended when progressive parenchymal changes are associated with mild to moderate symptoms. Steroid therapy, most often dexamethasone, may be initiated and tapered according to symptoms. When the dose of dexamethasone has been tapered to approximately 0.5mg daily, a taper of hydrocortisone will be initiated at approximately 25mg daily administered in divided doses. Dexamethasone will be discontinued within 2-3 days of the initiation of the hydrocortisone. Patients

IRB Approval date:

Rev. 3.2 dated: 1/19/2023 Protocol document date: 1/19/2023 St. Jude Children's Research Hospital

IRB NUMBER: Pro00004349

are not required to remain on steroid therapy during HBOT. In the setting of severe symptoms, medical oncology may be consulted to consider other measures including the use of bevacizumab.

#### 5.16 PET for Dose Verification of Proton Therapy

The number of PET activation studies will equal the number of proton treatment beams, which is estimated to be 3 for the majority of cases. On the day of the PET evaluation, the patient will be treated with a single beam corresponding to the activation beam under study. A separate plan may be developed to ensure the prescription dose to the target using a single beam on that day and that a critical normal tissue volume will not be compromised by the end of range uncertainty in RBE. The beam on time and duration for each of the single field treatment fractions will be recorded. The duration of the single beam fraction is estimated to be 10 to 15 minutes shorter than the conventional fraction. At the end of the single beam fraction, the patient will be transported to the PET-CT; estimated time required is 10 minutes. For PET attenuation correction and anatomic localization purposes, a CT of the cranium will be obtained; estimated time required is 5 minutes. The PET activation study will then be acquired for 30 minutes; the start time will be recorded. Based on the treatment plan, a Monte Carlo simulation of the positron activation locations and intensities will be created. The predicted image and acquired image will be compared and analyzed.

Alternatively, the patient may be treated with one beam, have the PET activation study and then complete the treatment with the remaining beams.

#### 6.0 REQUIRED EVALUATIONS, TESTS AND OBSERVATIONS

#### Instructions regarding the logistics of baseline evaluations

Surgery→enrollment→no surgery→ radiation therapy

If surgery was performed prior to enrollment and the patient does not require additional surgical intervention, similar to the preceding section, they should be enrolled on protocol and undergo baseline evaluation prior to radiation therapy.

Surgery→enrollment→surgery→ radiation therapy

Regardless of prior surgical history, patient who will undergo additional surgery should be enrolled on protocol and undergo baseline evaluation prior to surgery. If they are unable to complete the required baseline evaluations prior to surgery, partial evaluation will be accepted and the remaining baseline evaluations should be completed after surgery (i.e., partial evaluations prior to and following surgical intervention will be accepted). Investigators should consider repeating aspects of

IRB Approval date:

Rev. 3.2 dated: 1/19/2023 Protocol document date: 1/19/2023 St. Jude Children's Research Hospital

IRB NUMBER: Pro00004349

the baseline evaluation (e.g., diagnostic imaging, neurological examination, ophthalmology, etc.) that may be altered by surgery.

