To design this study we updated the experience at St. Jude Children's Research Hospital which included more than 47 children treated with fractionated reirradiation after 2000. The 3 year EFS and OS rates were 49% + 8% and 70% + 8%, respectively. More and less favorable subgroups were identified considering initial pattern of failure, duration of initial disease control, neuropathology at initial recurrence, extent of resection at initial recurrence. The value of this approach is further supported by the lack of significant surgery-related complications and acceptable late effects of irradiation. We retrospectively reviewed 32 patients who underwent surgery prior to a second course of irradiation, 43% had no surgical complications and facial nerve weakness in 6 patients (21%) lead the list of identifiable complications including CSF leak/pseudomeningocele (7%), lower cranial nerve weakness (7%), cerebellar ataxia (7%), hemiparesis (7%), tracheostomy/gastrostomy (3%) and subdural effusion requiring shunt (3%). Late complications have not been systematically reviewed for these patients.

The St. Jude approach to re-irradiation has been partly validated by investigators at the University of Toronto. From their institutional experience including the years 1986-2010, they analyzed the outcomes from 47 patients with recurrent disease [5]. Twenty-nine patients were treated with various combinations of surgery and/or chemotherapy and 18 were treated with a second course of irradiation. Re-irradiation included  $\geq$ 54Gy focal irradiation, with or without craniospinal irradiation and with or without surgery. Three-year OS was  $7\% \pm 6\%$  and  $81\% \pm 12\%$  for non-re-irradiated and re-irradiated patients (P < 0.0001). Time to second progression after re-irradiation was significantly longer than time to

Rev. 3.2 dated: 1/19/2023 Protocol document date: 1/19/2023 St. Jude Children's Research Hospital

IRB NUMBER: Pro00004349
IRB APPROVAL DATE: 02/01/2023

first progression. There was improved progression-free survival (PFS) for tumors with evidence of DNA damage (n=15; p=0.002). Overall treatment effects appeared limited. A decline in intellectual function was observed in assessed patients.

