#### 4.0 TREATMENT AND PLAN STRATIFICATION

#### 4.1 Overview

Patients will be enrolled on this protocol at St. Jude Children's Research Hospital (SJCRH) if they meet the eligibility criteria outlined in section 3.0. Patients may be enrolled before or after surgery performed at the time of recurrence. Enrollment prior to surgery is preferred to prospectively obtain peri-operative information about surgical morbidity and to facilitate the acquisition of tissue for biology studies. This protocol allows for co-enrollment on other protocols for recurrent ependymoma including those that might administer chemotherapy after irradiation. Chemotherapy concurrent with radiation therapy will not be allowed. Patients will be jointly evaluated by treatment teams representing neuro-oncology, radiation oncology and neurosurgery.

In the event that collaborative sites are allowed to join this trial, SJCRH will not be financially responsible for the cost of surgery, radiation therapy or follow-up for patients enrolled at collaborative sites. All patients are expected to undergo clinically indicated follow-up measures at the enrolling institution or at their routine point of care. Collaborative sites are expected to perform the research outlined in the protocol unless otherwise specified. The PI and protocol team at SJCRH will establish appropriate and legal (HIPAA) compliant communication with the enrolling institutions and the routine point of care for each patient.

Patients will be considered for enrollment if they have progressive disease after prior therapy that included surgery and focal irradiation with or without chemotherapy. There is no limit regarding the time interval from initial treatment failure to enrollment on this protocol which means that patients may choose other forms of therapy prior to enrollment on this protocol. Multiple episodes of progression will be allowed. The most common enrollment scenario will be the

Rev. 3.2 dated: 1/19/2023 IRB Approval date: St. Jude Children's Research Hospital IRB NUMBER: Pro00004349

patient who has been diagnosed with asymptomatic recurrence noted on surveillance neuroimaging. This patient will be consented for the study and will undergo pre-operative evaluations. Post-operatively, the studies necessary for treatment planning and to assess the impact of resection will be performed or repeated.

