\*Patient of childbearing potential requires a negative pregnancy test prior to starting treatment. (‡) should be repeated if clinically indicated following craniotomy. Imaging and clinical tests should be performed prior to radiation therapy; however, logistics may make it difficult to complete all exams prior to treatment. The principal investigator reserves the right to accept pre-irradiation testing within 16 weeks of the initiation of radiation therapy. PET-FDG and PET-methionine will also be done at time of progression or recurrence if prior to 24 months. Assessment/triage includes neck and abdomen circumference. #Edinburgh Handedness Inventory performed once. Patients who are unable to undergo standard audiometry may undergo ABR at the treating physician's discretion. Provocative screening will not be conducted for patients when the number of days off corticosteroids prior to the test date is less than the number of days on corticosteroids prior to discontinuance. MR spine may be performed more frequently for patients with spinal metastatic disease or at the discretion of the treating physician. Lumbar puncture for CSF cytology may be waived with PI approval based on contraindication or if adequate evaluation was performed within 3 weeks of enrollment. MET PET and FDG-PET scans not performed at 12, 24 or 36 month evaluation may be performed at a subsequent follow-up evaluation. All METPET studies will be whole-body regardless of the presence or absence of metastatic disease at the time of enrollment. Test will not be collected after July 1, 2020

Table 6.0.2 Evaluations at Baseline and Follow-up at St. Jude (Amendment 2.0)

Evaluations/Schedule 	Months after RT Start																
	0	3	6	9	12	15	18	21	24	27**	30	33**	36	42	48	54	60
Imaging																	
Diagnostic/Investigational	X	X	X	X	X	X	X	X	X	X	X	X	X	X	X	X	X
MR																	
MR Spine 	X				X				X				X		X		X
FDG-PET 	X				X				X				X				
PET-methionine 	X				X				X				X				
Lateral skull X-ray	X																
Bone Age/Q-CT/DEXA7	Х																
Clinical-Standard																	
Assessment/Triage	X	X	X	X	X	X	X	X	X	X	X	X	X	X	X	X	X
Physical Exam‡#	X	X	X	X	X	X	X	X	X	X	X	X	X	X	X	X	X
Lab: CBC‡	X	X	X	X	X	X	X	X	X	X	X	X	X	X	X	X	X
Lab: Chemistry‡	X	X	X	X	X	X	X	X	X	X	X	X	X	X	X	X	X
Lab: Endocrine Screen‡	X		X		X		X		X	X	X	X	X	X	X	X	X

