# 11.4 Statistical Analysis of Secondary Objective 1.2.3 Physical Performance

Objective: To describe physical performance and movement in children, adolescents and young adults with ependymoma treated with a second course of radiation.

Physical performance measures will be obtained at baseline, 12, 24, 36, 48 and 60 months. We will provide descriptive statistics of the following outcomes at each time point, and also provide the plots of individual profiles and mean profiles of the outcomes across time. The descriptive statistical analysis will be stratified by gender, age at diagnosis and total dose of brain radiation.

To model the outcomes' pattern and change over time, we will use generalized estimating equation (GEE) methodology with time as the main independent variable while adjusting for gender, age at diagnosis and total dose of brain radiation, including an interaction term if indicated. The assigned distribution and link function in each model will depend on the characteristic of the specific outcome as listed in next paragraph(s). The continuous measures will be modeled using normal distribution and identity link whereas the binary outcomes will be modeled using binomial distribution and logit link.

These analyses will be conducted at the conclusion of the trial and at an interim time point at which we have 15 patients in each stratum (a total of at least 45 patients) followed for 1 year. The results of the interim analyses will be submitted for presentation at an appropriate national scientific meeting, as well as to the CT-SRC.

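### The month-0 cognitive, physical-performance, sleep and quality-of-life test can fall before or after surgery, and the SAP neither defines which test is baseline nor models its timing

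*Combined protocol and SAP*

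**What the plan says.** **Enrollment.** Section 4.1 allows both orders: "Patients may be enrolled before or after surgery performed at the time of recurrence". It prefers enrollment before surgery. Section 4.2 expects that patients from other institutions will often have been operated on first.

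**Baseline timing.** Section 6.0 (logistics of baseline evaluations) gives three routes.
- Further surgery planned: "Regardless of prior surgical history, patient who will undergo additional surgery should be enrolled on protocol and undergo baseline evaluation prior to surgery".
- Surgery already done and none planned: "they should be enrolled on protocol and undergo baseline evaluation prior to radiation therapy".
- Battery not finished before surgery: "partial evaluation will be accepted and the remaining baseline evaluations should be completed after surgery". In other words, "partial evaluations prior to and following surgical intervention will be accepted".

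Section 6.6.2 lets the cognitive baseline run to 4 months after treatment starts. Sections 4.1 and 5.4 require no particular interval between surgery and irradiation.

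**Repeat after surgery.** In Tables 6.0.1 and 6.0.2 a double dagger marks items that "should be repeated if clinically indicated following craniotomy". It is on physical exam, CBC, chemistry, endocrine screen, audiometry, and the endocrine, neurology and ophthalmology rows. It is not on Psychology, Function Laboratory, Actigraphy or Questionnaires/QOL.

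**Analysis.** Section 11.2 presents its analyses as assessing adverse effects of irradiation, cognition included, and compares treatment groups. Section 11.3 compares focal with craniospinal treatment over time. Section 11.4 says "we will use generalized estimating equation (GEE) methodology with time as the main independent variable", adjusted for gender, age at diagnosis and brain dose.

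**The concern.** What a change score means depends on what happened between the two tests. After a pre-operative baseline, change to month 12 contains any lasting operative injury plus irradiation. After an early post-operative baseline it contains operative recovery plus irradiation, and recovery has the opposite sign to injury. After a baseline taken once irradiation has begun, part of the early irradiation effect is already in month 0.

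All of these enter one month-0 column, dated from the start of irradiation. If they are pooled without distinction, the curve estimates neither the effect of re-irradiation nor the effect of surgery plus re-irradiation. A focal versus craniospinal contrast is also distorted if the two groups differ in how often they are tested before surgery. Section 11.2 already accepts that these groups are not formed at random.

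The outcomes matter beyond description: Section 2.3 says cognitive monitoring could affect whether the treatment approach is judged acceptable.

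**Working it through.** The plan states no power, alpha or effect size for these endpoints, so there is no figure to reproduce. The check is first textual, then illustrative.

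**1. Is a post-operative repeat provided for?**

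| Source | What it provides | Reach |
|---|---|---|
| Tables 6.0.1 and 6.0.2 | Repeat mark absent from the four rows | All four |
| Section 4.2 | Firm statement that neurologic, endocrine and functional outcomes are reassessed after surgery | Function laboratory; QOL too, since Section 2.1 counts it as a functional outcome |
| Section 4.1 | Studies needed to judge the resection are performed or repeated; pre- and post-operative clinical assessments serve the secondary objectives | General; no test named |
| Section 6.0 | Investigators should consider repeating items that surgery may alter | Discretionary, open list; none of the four named |

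For physical performance and QOL, Section 4.2 and the tables conflict. For cognition and sleep, only general or discretionary wording could apply, so the gap is clearest there.

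**2. Does the analysis deal with it?** Section 11.2 (cognition) uses time, treatment group and unspecified clinical factors. Section 11.3 uses time, treatment and covariates chosen by BIC. Section 11.4 uses time, gender, age at diagnosis and brain dose. None names test timing relative to surgery or irradiation, and none says which of two tests is month 0. Section 4.1 concedes that surgery before enrollment limits the toxicity assessment, but no analysis uses that fact.

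**3. Form of the bias.** Let θ be the irradiation effect at a follow-up visit, f the share tested before surgery, s the net operative loss still present at that visit, and r the recovery since a post-operative test. The pooled mean change from month 0 is

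θ − f·s + (1 − f)·r.

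If r = 0, the spurious loss is f·s. If r > 0, the errors offset; at f = 0.5 they cancel when r = s, and the sign reverses when r > s. Direction therefore cannot be settled from the documents.

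**4. Illustration, pooled change.** All inputs here are assumptions: θ = 0, r = 0, SD of change 1, f = 0.25 to 0.75, s = 0.2 to 0.8 SD, two-sided test at 0.05. The sizes are n = 90 (the eligible number in Section 3.3) and n = 45.
- Bias: 0.25 × 0.2 = 0.05 SD to 0.75 × 0.8 = 0.60 SD.
- Midpoint: 0.5 × 0.5 = 0.25 SD. The standard error is √[(1 + f(1 − f)s²)/n] = √(1.0625/90) = 0.109, so z = 2.30 and false rejection is 63%. At n = 45 it is 37%.
- Over the whole grid, false rejection is 6% to 97% at n = 45 and 8% to 100% at n = 90.
- For the BOT-2 time trend in Section 11.4 (SD 10), an assumed net operative loss of 3 to 8 points with f = 0.5 gives 0.5 × 3 = 1.5 to 0.5 × 8 = 4.0 points.

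**5. Illustration, focal versus craniospinal (Sections 11.2 and 11.3 only).** Bias is the difference in f times s. For a difference of 0.1 to 0.5, this is 0.1 × 0.2 = 0.02 SD to 0.5 × 0.8 = 0.40 SD. With an assumed 45 per group, false rejection in that direction is 3% to 48% against a nominal 2.5%. At a difference of 0.3 and s = 0.5 it is 0.15 SD and 11%.

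**6. What the documents say about operative morbidity.** Section 2.1 reports of 32 re-operated patients that "43% had no surgical complications", so 57% had at least one. Ataxia and hemiparesis (7% each) bear on motor tests. Facial weakness (21%) and CSF leak or pseudomeningocele (7%) say little about cognition or sleep. This cannot be converted into s.

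**The case against.** **Retesting is not absent.** A reader might infer from the missing marks that anyone enrolled before surgery keeps a pre-operative baseline on all four tests. The documents do not support that. Section 4.2 commits to reassessing functional outcomes, Sections 4.1 and 6.0 leave room for other repeats, unfinished tests may be completed after surgery, and the cognitive window extends past the start of irradiation. This stands. What remains is a conflict between passages, and no rule for choosing the baseline when two tests exist.

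**The target may be the combined regimen.** Section 2.1 ranks toxicity of the whole regimen above attribution to its parts, and Section 11.4 has a descriptive objective. So a reader who infers that surgical loss will necessarily be reported as an irradiation effect goes too far. But if the combined regimen is the target, post-operative baselines are the wrong ones, because they omit operative injury. Pooling fails under either target.

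**Surgery may enter as a covariate.** Section 1.4.2 classes surgery and its complications as treatment factors, and Sections 11.2 and 11.3 leave covariates open. True, but type or extent of surgery does not record whether the baseline came before it, and Section 11.4 lists no surgical covariate.

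**The numbers are assumed.** Correct. Section 2.1 also describes significant surgery-related complications as lacking. A reader might carry the between-group illustration over to BOT-2, but Section 11.4 specifies no focal versus craniospinal comparison, so only the pooled time trend applies there.

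**Conclusion.** The concern holds in a limited form. Month 0 for cognition, physical performance, sleep and QOL may be pre-operative, post-operative or split, and for cognition may follow the start of irradiation. The provisions on retesting do not agree. Sections 11.2 to 11.4 define no analysis baseline and name no term for its timing, so modelled change mixes operative injury, operative recovery and irradiation.

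This matters most for cognition in Section 11.2, given its stated aim and its group comparison, and for the time trend in Section 11.4. The documents supply neither the share tested before surgery nor the operative shift. The illustrative ranges (0.05 to 0.60 SD pooled, 0.02 to 0.40 SD between groups) show scale only, assume no recovery, and could change sign. The affected outcomes are secondary and exploratory; the primary PFS and OS analyses are untouched. It is a worthwhile and cheap correction, not a threat to the trial's main conclusion.

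**What to change.** 1. Reconcile Sections 4.1, 4.2 and 6.0 with the repeat marks in Tables 6.0.1 and 6.0.2 and Appendix I, stating for each of the four test groups whether a post-operative test is expected.
2. From test, surgery and irradiation dates already held, classify each month-0 test as before or after the last surgery preceding irradiation, and as before or after the start of irradiation. Classify split batteries test by test.
3. In Sections 11.2 to 11.4, where a post-operative, pre-irradiation test exists, make it the baseline for irradiation effects.
4. For other patients, include a baseline-type indicator and its interaction with time, or report those with only a pre-operative test as a separate surgery-plus-irradiation series. The interaction keeps the series apart; it does not isolate irradiation in patients who lack a post-operative test.
5. Adjust the focal versus craniospinal comparisons in Sections 11.2 and 11.3 for baseline type.
6. Add a sensitivity analysis restricted to post-operative, pre-irradiation baselines.

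**Cost.** Derived timing variables and SAP wording; the analysis changes require no new test. The downside is some loss of precision, since about 90 patients are divided by baseline type, and more so in the restricted analysis.

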## **Instructions Regarding the Logistics of Follow-up Evaluations**

It is the intent of the investigators to perform follow-up evaluations to meet the primary objectives and research the exploratory aims (Table 6.0.2). Performance will be regularly monitored according to institutional guidelines and by the principal investigator. Principal Investigator will closely monitor compliance and, when necessary, will establish contact with primary care providers and engage home health nursing, to ensure completion of protocol-specified evaluations. It is a requirement that all patients enrolled at St. Jude undergo all evaluations. Patients enrolled at collaborative sites may have evaluation requirements tailored to the availability of local resources.

# **Sponsorship**

In the event that patients are enrolled at collaborative sites, the costs associated with research, treatment, follow-up and routine medical care will be the responsibility of the enrolling institution, patient and their family.

#### **Protocol Performance**

Despite the intent to adhere as closely as possible to the guidelines of this study, it is understood that unforeseeable circumstances may dictate postponement, cancellation or minor deviation in protocol guidelines because of intercurrent illness, logistical problems, and the absence of care providers or investigators, shortages in time and materials and lack of funding. Exceptions to the evaluation scheme will be made at the discretion of the Principal Investigator when clinical or logistical considerations preclude protocol-timely evaluation.

